2.3 Rationale

There is a growing need for anxiety treatments designed for young adults (ages 18-25 years of age). This age group uses mobile devices frequently, thus there is a clear opportunity to provide mobile treatment that is targeted for this age range. Mobile technology has been used to track mental health symptoms and also deliver mental-health services for adults with a variety of psychiatric symptoms (Dennis & O'Toole, 2014). Mobile-based interventions are advantageous in that they can provide momentary tailored interventions and collect real-time data about patient symptom severity (Burns et al. 2011). As a result, a goal of this work is to develop an effective mobile application for adolescents and young adults experiencing anxiety symptoms. The research team has an extensive background in understanding how adolescents and young adults may be more sensitive to certain types of rewards (i.e. social support), which will increase the patient's engagement with the mobile treatment.

The mobile application will utilize a version of a traditional "gold-standard" behavioral therapy approach to treat anxiety disorders - cognitive behavioral therapy (CBT) optimized for youth. Unlike many other types of psychotherapies, the standardized nature of CBT makes it compatible to be delivered in a web-based format (Spence et al., 2008). In addition, no current version of online CBT incorporates any behavioral interventions to enhance engagement and adherence to the web-based treatment protocol. The underlying scientific query is to understand the feasibility of online delivery of CBT and assess whether web-based incentive tools enhance treatment motivation and engagement, and assists with maintenance

of treatment gains and relapse prevention. This study lays the groundwork for developing and optimizing methods for maximizing engagement, and thus, treatment efficacy, in young adults with anxiety.

2.4 Risk/Benefit Assessment

Since this is a pilot study, and we are only trying to determine the feasibility of a mobile CBT program, subjects will not be using the CBT program in place of existing therapies. All existing therapeutic programs that subjects are part of will continue as normal. Thus, this study presents very minimal risk to participants. They may find the mobile CBT program boring or uninteresting, but since it is based in CBT theory, it will not make anxiety symptoms worse.

The optional MRI scan also presents minimal risk to participants. There will be no contrast used. There are no known side effects of an MRI scan. Risks include the potential for discomfort from MRI scanning. Some people (about one in ten) feel claustrophobic (fear closed spaces). Participants will be able to squeeze an emergency ball to communicate that they want to end the scan at any time.

Risks related to the EEG recording are also minimal. Participants may complete a computer task during the EEG that includes unpleasant (death, mutilation) and erotic images. These images are drawn from a widely used stimulus set (The International Affective Picture System (IAPS)) that has been used in many prior EEG studies, including [name] study with suicidal patients at WCM (protocol # 1603017115) as well as numerous studies outside of WCM (e.g. Albanese, 2019; Schupp, 2004; Weinberg, 2010; Sabatinelli, 2013). Risks include possible distress related to looking at emotional pictures or thinking about emotional situations; possible fatigue or boredom as a result of performing similar actions repeatedly; and possible mild skin irritation (redness) where the sensors contact the participant's scalp. Skin irritation in response to EEG recording is rare and temporary. Participants are offered breaks between the tasks and can choose to discontinue the EEG recording at any time.

In addition, the potential benefit of this study is that a mobile CBT program is created and is deemed feasible in this population. This is a potentially huge benefit, as mobile CBT programs could serve to enhance current CBT practices in patients with an anxiety disorder.

3. Subject Selection

3.1 Study Population

Subjects between 18 and 25 with a diagnosis of an anxiety disorder who meet the inclusion and exclusion criteria will be eligible for participation in this study.

3.2 Inclusion Criteria

Individuals who are between the ages of 18 and 25 and who have a primary diagnosis of an Anxiety Disorder, as determined by a score of 4 on the Clinical Severity Rating from the Anxiety Disorders Interview Schedule (ADIS), will be considered eligible to participate in this study.

3.3 Exclusion Criteria

Individuals who do not meet the cutoff score on the ADIS or who have a primary diagnosis other than an anxiety disorder will be excluded from participating in this study. Additionally, participants who are currently in cognitive behavioral therapy outside of the app or who have changed their dose of a psychiatric medication in the past 12 weeks will be excluded. Participants with the intent or plan to attempt suicide will be excluded from this study and provided referrals for treatment.

4. Registration Procedures

4.1 Patient Registration

Subjects will be registered within the WRG-CT as per the standard operating procedure for Subject Registration.

5. Study Procedures

5.1 Schedule of Evaluations

5.1.1 Screening Visit

This assessment will take place either in person, over the phone, or on a HIPAA-compliant virtual meeting platform. Decisions about how visits will take place will be made with participants, depending on safety and convenience.

- Anxiety Disorders Interview Schedule (ADIS) to get a Clinical Severity Rating (CSR) must be 4 or higher to receive a primary diagnosis of Anxiety Disorder, and no other psychiatric conditions can have a higher CSR).
- We will collect contact information so that we can follow up with the participant after the evaluation.
- We will also collect medication and psychiatric treatment information to determine study eligibility.

5.1.2 Treatment Phase

All study visits will take place either in person, over the phone, or on a HIPAA-compliant virtual meeting platform. Decisions about how visits will take place will be made with participants, depending on safety and convenience.

5.1.2.1 Visit 1: Baseline

- Participants are randomized to one of three incentive conditions (gain-framed points, loss-framed points, or social support). Participants in the social support condition will identify a person in their life who will receive

text message updates about their progress—or they can choose to have the study team receive the updates.

- Demographic Information
- Test of Premorbid Functioning for Wechsler Intelligence Scale for Adults (WAIS) unless completed within 18 months.
- Rumination Response Scale (RRS)
- Hamilton Rating Scale for Depression (HAM-D)
- Hamilton Rating Scale for Anxiety (HAM-A)
- Anxiety Sensitivity Index (ASI-3)
- Liebowitz Social Anxiety Scale (LSAS)
- Generalized Anxiety Disorder 7-item Scale (GAD-7)
- Patient Health Questionnaire 9 (PHQ-9)
- The Temporal Experience of Pleasure Scale (TEPS)
- Positive and Negative Affect Schedule (PANAS)
- Emotion Regulation Questionnaire (ERQ)
- Multidimensional Experiential Avoidance Questionnaire (MEAQ)
- Pittsburgh Sleep Quality Index (PSQI)
- World Health Organization Quality of Life short-form scale (WHOQOL-BREF)
- Life Events Scale for Students (LESS)
- Sensitivity to Punishment and Sensitivity to Reward Questionnaire (SPSRQ)
- Multidimensional Assessment of Interoceptive Awareness (MAIA)
- Digital Working Alliance Inventory (D-WAI)
- Medication Tracking
- Optional MRI Tasks: Points Incentive Delay Task, Social Incentive Delay Task
- Optional EEG

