1.1 Primary Objectives

We plan to develop an online cognitive behavioral therapy program, in collaboration with the Center for Health Incentives and Behavioral Economics (Wharton School) that can be integrated into their online platform, Way to Health (<https://www.waytohealth.org>) that has been developed over the past 10 years and automates many of the research functions necessary for conducting randomized controlled trials of behavior interventions and strategic telehealth programs in areas related to primary care medicine. The platform is an efficient, scalable, and low cost way to test behavioral interventions. To date, the platform has supported NIH-funded interventions that focus on medication adherence; weight loss; monitoring of blood sugar, blood pressure and weight; physical activity; smoking cessation; sleep and patient compliance.

One of the key features of the online platform (Way to Health) is its capacity to embed various incentive tools such as gamification and social support to the CBT intervention. In this context, these incentive components are novel to the delivery of any CBT treatment. A main hypothesis to be tested in this objective is whether the social support component will have a particular advantage to increase efficacy of CBT in this age group. This social support component will potentially extend the benefits of a group therapy approach, including connection with others, support, and encouragement. To test this hypothesis, we will randomize participants to one of three incentive structure conditions: a gain-framed incentive in which participants earn points for completing sessions, a loss-framed incentive in which they lose points for failing to complete sessions, and a social support incentive in which participants can identify a person they know to receive updates about their progress and support them throughout their time in the program. Participants will not be required to choose a person they know to receive updates about their use of the program; instead, they can choose to have a member of the study team serve as their social support if they are assigned to this condition.

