5.1.2.7 Visit 7 (+7 days from Visit 6): Endpoint

- *ADIS* sections for the anxiety disorder(s) the participant met criteria for at screening
- Rumination Response Scale (RRS)
- Hamilton Rating Scale for Depression (HAM-D)
- Hamilton Rating Scale for Anxiety (HAM-A)
- Generalized Anxiety Disorder 7-item Scale (GAD-7)
- Patient Health Questionnaire 9 (PHQ-9)
- The Temporal Experience of Pleasure Scale (TEPS)

Protocol # 1803019086
Version Date 12/27/2022

- Positive and Negative Affect Schedule (PANAS)
- Emotion Regulation Questionnaire (ERQ)
- Multidimensional Experiential Avoidance Questionnaire (MEAQ)

- Pittsburgh Sleep Quality Index (PSQI)
- World Health Organization Quality of Life short-form scale (WHOQOL-BREF)
- Life Events Scale for Students (LESS)
- Anxiety Sensitivity Index (ASI-3)
- Liebowitz Social Anxiety Scale (LSAS)
- Sensitivity to Punishment and Sensitivity to Reward Questionnaire (SPSRQ)
- Mobile Application Rating Scale: user version (uMARS)
- Digital Working Alliance Inventory (D-WAI)
- Optional MRI Tasks: Points Incentive Delay Task, Social Incentive Delay Task
- Optional EEG
- Medication Tracking
- Check in about how the app is working.

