11.4 Analysis of Endpoints

11.4.1 Analysis of Primary Endpoints

The primary purpose of the study is to compare change in anxious symptoms from baseline to Visit 7 (end of treatment with the mobile cognitive behavior mobile application) between the three incentive conditions. The primary measure of this endpoint will be the Hamilton Rating Scale for Anxiety (HAM-A), a 14-item questionnaire measure of the severity of anxiety symptoms. The items measure both psychic anxiety and somatic anxiety, where higher scores indicate a greater presence of symptoms and lower scores indicate mild to no anxiety symptoms. Secondary measures of this endpoint will be the Anxiety Sensitivity Index (ASI) and the Leibowitz Social Anxiety Scale (LSAS). The ASI is an 18-item scale containing three subscales measuring physical, cognitive, and social concerns regarding anxiety. Higher scores reflect greater self-reported concern and lower scores reflect little self-reported concern. The LSAS is a 24-item scale measuring fear and avoidance across social situations. Higher scores indicate greater fear and avoidance severity and lower scores indicate mild to no fear or avoidance.

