12.2.4 AE/SAE Follow Up

Please specify any follow up procedures for any AEs/SAEs that occur on study. Sample language is provided below in *italics*.

All SAEs and AEs reported during this study will be followed until resolution or until the investigator confirms that the AE/SAE has stabilized and no more follow-up is required. This requirement indicates that follow-up may be required for some events after the patient discontinues participation from the study.

13. Data and Safety Monitoring Plan (DSMP)

- We will be using REDCap, a secure web application, to manage participant data. Only individuals listed as co-investigators on the protocol will have access to this database.
- All data that is collected by the study team will be stored in the REDCap database. All questionnaire data collected for the study (see attachment) will be stored in the REDCap system.
- Participants can discontinue engagement in the study at their own discretion. The only foreseeable adverse events that may cause subjects to terminate protocol treatment is that they may get tired or bored of the tasks they asked to engage in on the mobile application.
- The researchers will report all adverse events and unanticipated problems to the monitoring board as soon as they occur.
- The monitoring entity will review data/events annually with the continuing review for the study.
- The researchers will terminate the protocol if they receive information from the monitoring board that they should do so.
- The monitoring entity's comments/reviews will be disseminated during the continuing review.
- The study application (CBT App) environment is stored and processed on the Weill Cornell ITS server with analytics information sent to Heap Analytics, and text message communications via Way to Health. Data on IP address, phone carrier, and city, as well as use of the app is collected on these platforms.

These are companies outside of Weill Cornell that will have access to participants' personal information. If these data are further disclosed by them or their business partners, it may no longer be covered under the privacy protections. Text messaging does not provide a completely secure and confidential means of communication. Participants are made aware of the risks that are inherent in using text messaging.

References

Please provide the citations for all publications referenced in the text.

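### No masked or independent HAM-A assessor is specified in any arm, and in the social support arm a study team member may also be the support person, so assessment bias could differ by arm.

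*Combined protocol and SAP*

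**What the plan says.** **The support role.** Section 1.1 says that participants need not pick someone they know; instead "they can choose to have a member of the study team serve as their social support if they are assigned to this condition". Section 5.1.2.1 repeats the option for the text updates: "or they can choose to have the study team receive the updates". Neither points arm has an equivalent. Section 1.1 also makes a particular advantage of social support a main hypothesis.

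**The primary outcome.** Section 11.4.1 sets out to "compare change in anxious symptoms from baseline to Visit 7" between the three conditions, and adds: "The primary measure of this endpoint will be the Hamilton Rating Scale for Anxiety (HAM-A), a 14-item questionnaire measure". The HAM-A is listed at Visits 1, 4, 7 and 8. The ADIS sections for the participant's anxiety disorder(s) are repeated at Visit 7.

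**Who collects it.** Section 13 says "All data that is collected by the study team will be stored in the REDCap database". No section says who administers or scores the HAM-A. None mentions masking, an independent rater, or any division between staff who support and staff who assess.

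**Routes to unmasking.** The item "Check in about how the app is working" is listed at every visit from 2 to 8, for all arms. In Section 5.1.2.1 randomization is the first item at Visit 1, and the HAM-A is listed after it.

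**The concern.** The trial's main contrast is between incentive conditions on an anxiety score. In one condition the study team may be part of the intervention, and the plan does not keep that role away from outcome collection.

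Two mechanisms could follow. If the HAM-A is rated by an interviewer, a supporter's expectations may colour the rating. If participants complete it themselves, those who chose staff may under-report symptoms to the team that has been supporting them. Either would lower Visit 7 scores in some social support participants, with no matching supporter role in the points arms. The comparison would then mix any true effect with a measurement difference that points the same way as the hypothesis.

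Allocation can also become known in every arm through the app check-ins. Because the endpoint is a change score, a baseline HAM-A taken with allocation known would add to the problem.

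**Working it through.** The plan gives no alpha, power, SD, effect size or allocation ratio, so it has no figure of its own to reproduce here. The check has two parts.

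**1. Is the overlap excluded anywhere?**

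| Question | What the plan gives |
|---|---|
| May staff be the supporter? | Yes, in the social support arm, at the participant's choice (1.1, 5.1.2.1) |
| Who takes the HAM-A? | Not named; collection is by the study team in general terms (13) |
| Must supporter and assessor differ? | Not stated |
| Is the assessor masked? | Not stated for any arm |
| Can staff learn the arm? | Yes, through app check-ins at Visits 2 to 8 in all arms |

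The overlap is thus permitted by silence. It is not prescribed.

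**2. How much could it matter?** Illustration only.

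Inputs:
- N = 120 (Protocol Summary; Section 11.2 expects 120 to complete). Equal allocation is assumed, giving 120/3 = 40 per arm.
- Two-sided 5% comparison of social support with one points arm (assumed).
- HAM-A change in SD units (SD = 1), with no true difference.
- Share choosing staff, q: 25%, 50% or 100% (assumed).
- Bias in each affected participant, b: 0.2, 0.3 or 0.5 SD (assumed).

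Formulas:
- Arm-average shift s = q × b.
- SE of the difference = √(2/40) = 0.2236 SD.
- Rejection rate = P(|Z + s/SE| > 1.96).

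For b = 0.3:
- q = 25%: s = 0.075, s/SE = 0.335, rate 6.3%.
- q = 50%: s = 0.15, s/SE = 0.671, rate 10.3%.
- q = 100%: s = 0.30, s/SE = 1.342, rate 26.9%.

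Full grid:

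| Share choosing staff | b = 0.2 | b = 0.3 | b = 0.5 |
|---|---|---|---|
| 25% | 5.6% | 6.3% | 8.7% |
| 50% | 7.3% | 10.3% | 20.1% |
| 100% | 14.6% | 26.9% | 60.9% |

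For scale in points: if the SD of HAM-A change were 7 (assumed; range 5 to 9), a bias of 0.3 SD would be 0.3 × 7 = 2.1 points (1.5 to 2.7).

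For comparison, the true difference detectable with 80% power at 40 per arm is (1.960 + 0.842) × 0.2236 = 0.63 SD. An arm-average shift of 0.15 SD is about a quarter of that (0.15/0.63 = 0.24).

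**The case against.** The other side has real force on several points.

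- **Masking.** A reader might infer that the outcome is unmasked in the social support arm alone. The documents do not support that: no masking is described in any arm, and the check-ins can reveal allocation in all three. Only the staff supporter role is confined to one arm.
- **Same person.** A reader might infer that the supporter does take the HAM-A. No section says so. The plan merely fails to prevent it.
- **Rater.** Section 11.4.1 calls the HAM-A a questionnaire, and its mode of administration is not stated. Rater expectation needs a rater. This weakens the first mechanism but leaves the second, and the Visit 7 ADIS is an interview by name.
- **Contact in all arms.** Every participant has weekly check-ins, so rapport with staff and a wish to please can arise in every arm. What could differ is the extra effect of the supporter role, and the plan says little about what a staff supporter does.
- **Uptake.** Staff support is an alternative to a personal contact. If few choose it, the arm-average shift is small.
- **Cross-check.** Section 11.4.1 describes the ASI as self-reported, so it would help against rater expectation. It would not help against under-reporting by participants.

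These points narrow the concern and make its size uncertain. None supplies the missing safeguard.

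**Conclusion.** The concern holds as a gap in the plan, not as a demonstrated bias. No masked or independent HAM-A assessor is specified in any arm. In the social support arm only, a team member may be the supporter and may also collect that participant's HAM-A or Visit 7 ADIS. Assessment bias could therefore differ by arm and could favour the hypothesised arm.

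The size cannot be derived from the documents. With 40 per arm and a 0.3 SD bias, both assumed, the false-positive rate against one points arm is about 6%, 10% or 27% when 25%, 50% or all of the arm choose staff. The last figure is the extreme of uptake and should not be read as an expected value. Nor do the documents show that scores would fall in this arm; that direction is plausible but not established.

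The change is worth making because it is cheap and has to be in place before the data are collected. As written, the plan does not require anyone to record who served as supporter, so even a descriptive check afterwards is not assured.

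**What to change.** (a) State in Sections 5.1.2.1, 5.1.2.7 and 11.4.1 that a team member who serves as a participant's support person, or receives that participant's updates, does not collect that participant's HAM-A or ADIS. Say in 11.4.1 who administers and scores the HAM-A.

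(b) Take the baseline HAM-A before allocation is revealed. At Visits 4, 7 and 8 take it before the uMARS and the app check-in, by an existing team member not shown the arm where staffing allows, and note any unmasking. The condition matters because the documents give no staffing numbers.

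(c) Record for each social support participant whether the supporter is a personal contact or staff. Report the primary comparison without staff-supported participants as a descriptive check only. Supporter type is chosen after randomization, and removing participants from one arm on that basis leaves groups that are no longer strictly comparable.

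The cost is protocol wording, one recorded item and rota planning, with no added visits. The downsides are less flexible scheduling and occasional unmasking that has to be documented.

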5.1.2.2 Visit 2 (+7 days from Visit 1)

- Generalized Anxiety Disorder 7-item Scale (GAD-7)
- Patient Health Questionnaire 9 (PHQ-9)
- Mobile Application Rating Scale: user version (uMARS)
- Medication Tracking
- Check in about how the app is working.

5.1.2.3 Visit 3 (+7 days from Visit 2)

- Generalized Anxiety Disorder 7-item Scale (GAD-7)
- Patient Health Questionnaire 9 (PHQ-9)
- Medication Tracking
- Check in about how the app is working.

5.1.2.4 Visit 4 (+7 days from Visit 3): Midpoint

Protocol # 1803019086
Version Date 12/27/2022

- Rumination Response Scale (RRS)
- Hamilton Rating Scale for Depression (HAM-D)
- Hamilton Rating Scale for Anxiety (HAM-A)

- Generalized Anxiety Disorder 7-item Scale (GAD-7)
- Patient Health Questionnaire 9 (PHQ-9)
- The Temporal Experience of Pleasure Scale (TEPS)
- Positive and Negative Affect Schedule (PANAS)
- Emotion Regulation Questionnaire (ERQ)
- Multidimensional Experiential Avoidance Questionnaire (MEAQ)
- Pittsburgh Sleep Quality Index (PSQI)
- World Health Organization Quality of Life short-form scale (WHOQOL-BREF)
- Life Events Scale for Students (LESS)
- Anxiety Sensitivity Index (ASI-3)
- Liebowitz Social Anxiety Scale (LSAS)
- Sensitivity to Punishment and Sensitivity to Reward Questionnaire (SPSRQ)
- Mobile Application Rating Scale: user version (uMARS)
- Digital Working Alliance Inventory (D-WAI)
- Medication Tracking

- Check in about how the app is working.

5.1.2. 5 Visit 5 (+7 days from Visit 4)

- Generalized Anxiety Disorder 7-item Scale (GAD-7)
- Patient Health Questionnaire 9 (PHQ-9)
- Medication Tracking
- Check in about how the app is working.

5.1.2. 6 Visit 6 (+7 days from Visit 5)

- Generalized Anxiety Disorder 7-item Scale (GAD-7)
- Patient Health Questionnaire 9 (PHQ-9)
- Medication Tracking
- Check in about how the app is working.

